3. EXPERIMENTAL PLAN

3.1 Study Design

This is a randomized, double-blind, placebo-controlled, parallel-group study in subjects with episodic migraines. This study will evaluate the efficacy of AMG 334 as measured by inhibition of PACAP-38 induced migraine-like attacks after a single dose of AMG 334. Migraine-like attacks (MLA) will be defined as attacks fulfilling one of the two criteria:

(1) Headache fulfilling criteria C and D for migraine without aura (IHS 2004)

- C. Headache has at least two of the following characteristics:
 - unilateral location
 - pulsating quality
 - moderate or severe pain intensity (≥ 4 on headache questionnaire)
 - aggravation by or causing avoidance of routine physical activity

D. During headache at least one of the following:

- nausea and/or vomiting
- photophobia and phonophobia

(2) Headache described as mimicking usual migraine attack treated with triptan.

Part A: PACAP-38 Dose Selection Phase: There are a number of published clinical studies in which pituitary adenylate cyclase-activating polypeptide-38 (PACAP-38) was used to trigger MLA in migraneurs (Schytz et al, Brain 2009; Amin et al, Cephalagia 2011; Amin, Brain 2014). In those studies, 10 pmol/kg/min over 20 minutes (total dose 200 pmol/kg) was administered. Approximately 90% of migraineurs experienced a headache and approximately 66% of the same migraineurs experienced MLA with a median time of headache onset of 4 hours, though the half-life of PACAP-38 is only 3.5 minutes. As PACAP-38 is involved in various biological processes, including sensory processing, vasodilation, inflammation, and nociceptive transmission (Dickinson et al., 1999; Vaudry et al., 2000), nearly all healthy subjects and migraineurs also experienced the expected adverse events of flushing and heat sensation, along with a transient elevation in heart rate and blood pressure (Birk et al, Regulatory Peptides 2007; Schytz et al, Brain 2009; Amin et al, Cephalagia 2011; Amin, Brain 2014) (see Investigator Brochure for details).

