6.9 Excluded Treatments and/or Procedures During Study Period

Use of any over-the-counter or prescription medications within the 14 days or 5 half-lives (whichever is longer), prior to receiving the first dose of AMG 334 or PACAP-38. Simple

analgesics including NSAIDs will be allowed, but not within 48 hours prior to infusion of PACAP38. Subjects are not allowed to be on preventive therapies for migraine.

Paracetamol (up to 2 g per day) for analgesia and hormone replacement therapy (eg, estrogen, thyroid) will be allowed. Simple analgesics including NSAIDs will be allowed, but not within 48 hours prior infusion of PACAP-38. Subjects are allowed to take rescue medication for a migraine attack (their usual migraine treatment or a triptan) and for adverse events, such as emesis and allergic reactions (clemastin 2 mg, prednisolone 100 mg). Any herbal medicines (eg, St. John's wort), vitamins, and supplements consumed by the subject within 21 days prior to receiving the first dose of AMG 334, and continuing use if applicable, will be reviewed by the investigator and the Amgen Medical Monitor. Written documentation of this review and Amgen acknowledgement are required for subject participation. Refer to Section 6.5 for guidance on concomitant therapy.

- 7. STUDY PROCEDURES
- 7.1 Schedule of Assessments

Activity	Screeni	ng	Treatment Period											Fo	EOS Visit					
Study Day	-21 to -2	-1	Day 1 ^a						Dav	Day 9	Day 10	Day 29	Day 57	85						
Time (in hours)			Pre- Dose	0	0.5	1	Pre- Dose	0	0.25	0.5	1	2	3	4	8	24	48			
General & Safety Assessments	F	1	1	1	1		1				٩	I	1		1	I	٩	٩		
Informed Consent	Х						h													
Residency							X	Х	Х	Х	Х	Х	Х	Х	Х	Х				
Medical History	X																			
Body Weight	X	Х																		Х
Height	Х						~			~		~				~				
Vital Signs (BP, HR, RR, TEMP) ^g	X	Х	Х		Х	Х	X ^g		Х	X g	Х	Xg	Х	Х	Х	Xg	Х	Х	Х	Х
Physical Examination	Х	Х																Х		Х
Neurological Examination	Х		Х				Х									Х		Х		Х
12-lead Electrocardiogram ^c	X		Х		Х		Х			Х	Х	Х		Х	Х	Х	Х			Х
Adverse Event Recording				Х	Х	Х	Х	Х	Х	Х	Х	Х	Х	Х	Х	Х	Х	Х	Х	Х
Serious Adverse Event	Х	Х	Х	Х	Х	Х	Х	Х	Х	Х	Х	Х	Х	Х	Х	Х	Х	Х	Х	Х
Concomitant Medications	Х	Х	Х	Х	Х	Х	Х	Х	Х	Х	Х	Х	Х	Х	Х	Х	Х	Х	Х	Х
Laboratory Assessments	-											-								
Creatinine Clearance ⁱ	Х	х					х									Х				
Clinical Chemistry	Х	Х					Х									Х				Х
Clinical Hematology	Х	Х					Х									Х				Х
Urinalysis '	Х	Х					Х									Х				Х

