Drug, Alcohol & Cotinine Screen	Х	Xj					X ^{h j}													
HIV, HepCAb, HBsAg, HBcAb	Х																			
Postmenopausal status test, (females only) ^k	Х																			
Cardiac Enzymes	Х	Х					Х					Х		Х	Х	Х				
Pregnancy Test (females only) ^d	Х	Х					Х													Х
Questionnaires																				
Headache Questionnaire		Х						Х	Х	Х	Х	Х	Х	Х	Х	Х				
Columbia-Suicide Severity Rating Scale	Х	Х	х				х									Х		Х	Х	Х

Table 2. Schedule of Assessments For Part B: Randomized (AMG 334 or Placebo) Subjects

Footnotes are defined on the next page of table

Page 1 of 2

Activity	Screeni	Treatment Period											Fo	EOS Visit						
Study Day	-21 to -2	-1		Day 1 ^ª				Day 8 ^{b f g}										Day 29	Day 57	85
Time (in hours)			Pre- Dose	0	0.5	1	Pre- Dose	0	0.25	0.5	1	2	3	4	8	24	48			
Dosing																				
Study Drug Administration				Х																
Challenge-agent (PACAP-38) ^f								X ^f												
Pharmacokinetic and Other Blood	Samples																			
Antibody Sample Collection			Х															Х	Х	Х
AMG 334 Serum PK Collection ^e			Х			Х	Х			X e								Х	Х	Х
CGRP Plasma Collection			Х				Х		Х	Х										Х
PACAP-38 Plasma Collection							Х		Х	Х										
Cell Pellet for Pharmacogenetics			Х																	

Table 2. Schedule of Assessments For Part B: Randomized (AMG 334 or Placebo) Subjects

Page 2 of 2

Abbreviations: ECG = electrocardiogram; EOS = end of study; FSH = follicle-stimulating hormone; HepBsAg = hepatitis B surface antigen; HepCAb = hepatitis C antibody; HBcAB = hepatitis B core antibody; HIV = human immunodeficiency virus; PK = pharmacokinetic

^{a.} Subjects will return to the research facility one day prior to investigational product administration (Day -1), at which time baseline procedures will be completed. After completion of all pre-dose and baseline laboratory and vital sign procedures on the day of dosing (Day 1), subjects will receive AMG 334 or matching placebo. -Subjects will reside at the research facility for at least 1 hour and then be discharged home.

^{b.} Subjects will return to the research facility on Day 8, at which time pre-dose procedures will be completed. After completion of pre-dose procedures on Day 8, subjects will receive PACAP-38. Subjects will reside at the research facility for at least 24 hours post PACAP-38 infusion and then be discharged home.

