^{c.} At Screening ECGs will be performed in a standardized method, in triplicate, and approximately 30 seconds apart, prior to blood draws or other invasive procedures. Single ECGs will be performed from Day 1 to EOS.

^{d.} A serum pregnancy test will be performed at screening. Serum or highly sensitive urine (cutoff of 20 mlU/L) pregnancy tests will be performed at Day -1, Day 8 Pre-Dose and EOS.

^{e.} Flexible PK sampling point, that could be collected at any time on Day 8 between pre-PACAP-38 to 2 hours post-PACAP-38 administration.

^{f.} PACAP-38 should not be administered if subject reports having a headache within 72 hours prior to Day 8. Subject should return to the research facility from Day 8 – Day 12 for PACAP-38 administration.

⁹ Rectal temperature will be collected after obtaining blood pressure, prior to PACAP-38 infusion and post PACAP-38 infusion at Hours 0.5, 2 and 24.

^{h.} Negative drug, alcohol and cotinine test is required prior to PACAP-38 dose. Positive results will be reviewed between the PI and MM on a case by case basis.

¹ Laboratory results required prior to AMG 334 and PACAP-38 dose. Abnormal lab results will be reviewed between the PI and MM on a case by case basis prior to PACAP-38 dose.

^{j.} A reliable urine drug test performed at the site is allowed.

^k Additional serum will be collected for an FSH, LH, or estradiol test for postmenopausal women at screening as defined in Section 7.2.22.

¹ Cardiac enzymes include CPK-MB and Troponin I or Troponin T.

	0		The first of Parts I					Follo	w-Up	EOS				
Activity	Screenin	ng										Per		VISIT
Study Day	-21 to -2	-1										Day 2	Day 3	Day 8
Time (in nours)			Pre-Dose	0	0.25	0.5	1	2	3	4	ð	24	48	
General & Safety Assessments	X	1	1			-	1	1		1			 	
Informed Consent	X				X		V	V	V	V	X			
Residency		-	X	X	X	X	Х	Х	Х	Х	Х	X		
Medical History	X													
Body Weight	X	X												X
Height	X		a a d					a d				d		
Vital Signs (BP, HR, RR, TEMP) ^u	Х	Х	Xu		Х	Χu	Х	Xu	Х	Х	Х	Χu	Х	Х
Physical Examination	Х	Х												Х
Neurological Examination	Х		Х									Х		Х
12-lead Electrocardiogram ^a	Х		Х			Х	Х	Х		Х	Х	Х	Х	Х
Adverse Event Recording				Х	Х	Х	Х	Х	Х	Х	Х	Х	Х	Х
Serious Adverse Event	Х	Х	Х	Х	Х	Х	Х	Х	Х	Х	Х	Х	Х	Х
Concomitant Medications	Х	Х	Х	Х	Х	Х	Х	Х	Х	Х	Х	Х	Х	Х
Laboratory Assessments														
Creatinine Clearance	Х	Х										Х		
Clinical Chemistry	Х	Х										Х		Х
Clinical Hematology	Х	Х										Х		Х
Urinalysis	Х	Х										Х		Х

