10.5.4 Exploratory Endpoints

10.5.4.1 Migraine-like Attacks (MLA) and Headaches

The reduction in severity by AMG 334 of MLA and headaches within 24 hours after infusion of PACAP-38 will be assessed and summarised based on a severity score (0-10; 0=pain free; 10=extreme pain). For MLA and headaches separately severity scores will be analysed using a repeated measure analysis of variance model.

Independent variables will be treatment, hour and treatment by hour interaction. Subject will serve as a random effect. For each treatment by hour combination, least square means, ratio to Placebo, 95% confidence intervals and p values for the null hypothesis of no difference from placebo will be presented. Graphical summaries of severity scores will also be provided. In addition, descriptive statistics will be provided for the duration of MLA and headaches.

Descriptive summaries of measured characteristics of MLA and headaches, such as localization and accompanying symptoms and pre-monitory symptoms, within 24 hours after infusion with PACAP-38 will be presented for each treatment group.

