On Phase 1 Day 1 (Challenge Period), PACAP-38 naïve subjects will receive the dose of PACAP-38 determined from the PACAP-38 Dose Selection Phase (part A) and will be followed until Day 8. For subjects that do not experience a MLA within 24 hours following PACAP-38 administration (non-responders), Day 8 will be their End of Study (EOS) visit. Those subjects who experience a MLA within 24 hours following PACAP-38 (responders) will be randomized to receive 140 mg IV AMG 334 over 30 minutes or placebo on Phase 2 Day 1 (Treatment Period), in a one to one allocation ratio. On Day 8, the PACAP-38 responders will be administered the dose of PACAP-38 determined from the PACAP-38 Dose Selection Phase (part A).

All subjects will remain in-house for 24 hours of observation following PACAP-38 infusion. Subjects (respectively PACAP-38 responders from part A and PACAP-naïve subjects) will be followed until Day 85.

Subjects will be monitored and asked questions from the headache questionnaire, as per the Schedule of Assessment in Table 2 of Protocol Amendment 4, to determine if they have experienced a MLA. Previous challenge studies have shown that for migraineurs the median onset of a MLA is within 4 hours with some patients experiencing a MLA as late as 12 hours following PACAP-38 infusion. Therefore, a

Statistical Analysis Plan: 20140207

Dated: 17 May 2017 Page 10

[figure not shown]
headache questionnaire covering the 24 hours after infusion will ensure capture of all the PACAP-38 induced MLAs. After 24 hours of data from the first 16 randomized (AMG 334 or Placebo) subjects challenged with PACAP-38 is available, an interim analysis will be conducted to determine if challenge rates are comparable to historical rates (~66%) and if AMG 334 has greater efficacy than placebo. If AMG 334 is found to completely block PACAP-38 induced migraines, or have the same efficacy as placebo, the study will be terminated. Otherwise, approximately 20 randomized (AMG 334 or Placebo) subjects will be added.

The overall study design is described in the study schema below:

Statistical Analysis Plan: 20140207

Date: 17 May 2017

Abbreviations:

[figure not shown]
DLRM = Dose Level Review Meeting IV = Intravenous

Page 11

Statistical Analysis Plan: 20140207

Date: 17 May 2017 Page 12

Statistical Analysis Plan: 20140207

Date: 17 May 2017 Page 13

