10.7 Exploratory Endpoint(s)

10.7.1 Migraine-like Attacks (MLA) and Headaches

The reduction in severity of MLA and headaches by AMG 334 within 24 hours after infusion of PACAP-38 on day 8 will be assessed and summarised based on a severity score (0-10; 0=pain free; 10=extreme pain). Severity of MLA and headaches will be analysed separately using a repeated measure analysis of variance model. Independent variables will be treatment, hour, and treatment by hour interaction. Subject will serve as a random effect. For each treatment by hour combination, least square means, ratio to placebo, 95% confidence intervals and corresponding nominal p-values for the null hypothesis of no difference from placebo will be presented. Graphical summaries of severity scores will also be provided. For SAS code, see Appendix A1.

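### The exploratory severity analysis reports a ratio to placebo of 0–10 pain scores at each hour, and that ratio can be undefined at 0–1 h, and possibly at 24 h, when the placebo mean is zero or close to it

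*SAP*

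**What the plan says.** SAP 10.7.1 models severity of MLAs and of headaches separately, with a repeated-measures analysis of variance on the 0–10 pain score. The terms are treatment, hour and their interaction, with subject as a random effect. The planned display for every treatment-by-hour cell is "For each treatment by hour combination, least square means, ratio to placebo, 95% confidence intervals and corresponding nominal p-values", and the p-values are for no difference from placebo. Protocol 10.5.4.1 plans the same: "least square means, ratio to Placebo, 95% confidence intervals and p values for the null hypothesis of no difference from placebo".

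The following passages bear on the size of the placebo mean at each hour:

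- **Schedule.** Protocol Table 2 schedules the "Headache Questionnaire" on Day 8 at 0, 0.25, 0.5, 1, 2, 3, 4, 8 and 24 h. Protocol 7.2 allows 30 minutes either side.
- **State before challenge.** Table 2, footnote f: "PACAP-38 should not be administered if subject reports having a headache within 72 hours prior to Day 8".
- **Onset.** Protocol 3.1 reports that, in earlier studies, migraineurs "experienced MLA with a median time of headache onset of 4 hours". SAP 3.1 says "the median onset of a MLA is within 4 hours".
- **Resolution.** Protocol 6.9: "Subjects are allowed to take rescue medication for a migraine attack". The questionnaire in Appendix D also asks how long complete relief took.

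Two general clauses in the SAP are relevant. Section 10.1 allows differences or ratios as applicable and calls the outputs descriptive. Section 9.6 allows transformations or non-parametric methods if required. Section 10.7.1 refers to Appendix A1 for the code, but only the appendix heading is visible in the copy reviewed.

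**The concern.** A ratio of means needs a denominator clearly away from zero. Here zero is a legitimate score, and at the early scheduled times it may be the commonest one. If every placebo subject scores 0 at some hour, the placebo least square mean is 0 and the ratio does not exist. If one or two have pain, the ratio exists but rests on those one or two scores, and its confidence interval may have no finite limit. Taking logs does not help, because the log of a zero score is also undefined.

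The estimate also does not match the test printed beside it: the p-value is for no difference, while the estimate is a ratio.

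At the affected hours the named effect estimate and its interval would be missing or uninterpretable. The least square means and p-values would still be reported, so a reader could subtract the means but would have no interval for the result.

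**Working it through.** The documents give no figure for this analysis, so there is none to reproduce. The check asks how often the ratio fails, given the share of placebo subjects in pain at an hour.

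**Inputs.** Placebo n is 8 (stop at the interim) or 18 (full size), from SAP 8.2. The share in pain, p, is not in either document and is varied.

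**1. Ratio undefined.** With complete data and a full treatment-by-hour model, the cell least square mean equals the raw cell mean. It is zero only if all n scores are zero:

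P(placebo mean = 0) = (1 − p)^n

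| Share in pain, p | n = 18 | n = 8 |
|---|---|---|
| 5% | 0.95^18 = 0.397 | 0.95^8 = 0.663 |
| 10% | 0.90^18 = 0.150 | 0.90^8 = 0.430 |
| 20% | 0.80^18 = 0.018 | 0.80^8 = 0.168 |
| 40% | 0.60^18 = 0.0001 | 0.60^8 = 0.017 |

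To hold this risk at 5%, the share in pain must be 1 − 0.05^(1/18) = 0.153 with 18 per arm, or 1 − 0.05^(1/8) = 0.312 with 8 per arm.

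**2. Linking p to the hour.** Assume exponential onset with median m hours among the share s who ever get a headache: p = s × (1 − 2^(−h/m)). With s = 0.9 (the historical headache rate in Protocol 3.1) and m = 4:

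| Hour | p | Mean zero, n = 18 | Mean zero, n = 8 |
|---|---|---|---|
| 0.25 | 0.038 | 0.50 | 0.73 |
| 0.5 | 0.075 | 0.25 | 0.54 |
| 1 | 0.143 | 0.06 | 0.29 |

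Varying s over 0.66, 0.9 and 1.0 and m over 1, 2 and 4 h gives, at 0.25 h, 0.04–0.60 (n = 18) and 0.25–0.80 (n = 8). At 1 h it gives below 0.001 to 0.14 (n = 18) and 0.004–0.41 (n = 8). At hour 0, if all placebo subjects are pain free as the 72-hour rule implies, the ratio is undefined; it is 0/0 if both arms are zero.

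**3. Interval unbounded.** Neither document names the interval method. A Fieller interval for a ratio is unbounded when the placebo mean is not distinguishable from zero, that is, when mean ≤ t(0.975, 2n − 2) × SE. The simulation used 40,000 trials per cell, with equal arms, variance pooled over arms, and non-zero pain drawn from N(4, 2), rounded and limited to 1–10:

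| Share in pain | n = 18 | n = 8 |
|---|---|---|
| 10% | 83% | 96% |
| 20% | 58% | 87% |
| 40% | 14% | 60% |

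A second simulation, with pain uniform on 1–6 and only the placebo-arm variance, gave 70% (n = 18) and 97% (n = 8) at 20% in pain, and 2% and 55% at 50% in pain.

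**4. 24 h.** With one variance pooled over hours and 18 per arm, the interval is unbounded in 93% of trials if 10% are still in pain at 24 h, and in 43% if 30% are.

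**5. The difference instead.** With 18 per arm, 10% in pain and no treatment effect, the difference in means has a 95% range of −0.9 to +0.9 points. Among trials where the ratio exists, its 95% range is 0 to 7.0.

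**The case against.** The best counter-argument is that the problem depends on things not visible. The Appendix A1 code might define the scale, the hours and the handling of zeros, and its absence from this copy is not a fault of the plan. Separate models for MLAs and headaches suggest some selection of scores. If only scores taken during pain enter, zeros drop out and the point no longer applies in this form. If subjects with an event enter with all their scores, zeros before onset remain, but n is no longer 8 or 18.

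Other limits also stand. Severity is described as within 24 hours after infusion, so hour 0 may be left out, and the 30-minute window means a nominal hour-0 score need not precede the infusion. A median onset within 4 hours is an upper bound, and the onset data come from studies at 200 pmol/kg. At 1 h with 18 per arm, an exactly zero mean is unlikely (at most 0.14 above). The 24 h evidence shows that relief is possible, not how common it is. The schedule, 72-hour rule, rescue text and questionnaire come from Protocol Amendment 3, while the SAP follows Amendment 4 and randomises only PACAP-38 responders, which the assumed shares ignore. The ratio is usable at 4 and 8 h with 18 per arm: the by-hour simulation gave unbounded intervals in about 1% of trials or fewer there, with 50–60% in pain.

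These points limit how often the ratio fails, but they do not remove the failure. The general clauses in SAP 9.6 and 10.1 do not withdraw the ratio that 10.7.1 names, and reporting a cell as not estimable leaves that hour without an effect estimate.

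**Conclusion.** The concern holds as a statement of what can happen: at 0–1 h, and possibly at 24 h, the named ratio can be undefined or have an unbounded interval. At 10% of placebo subjects in pain, the mean is exactly zero in 15% of trials with 18 per arm and 43% with 8 per arm. At 40% in pain this falls to 0.01% and 1.7%. These figures assume that pain-free scores enter the model, that all placebo subjects contribute, and that the share in pain is as stated. The interval figures also assume the Fieller method.

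This is an optional improvement, held with medium confidence because the code cannot be seen. The endpoint is exploratory, SAP 10.1 treats the outputs as descriptive, no decision rule uses severity, and the primary Fisher test is unaffected.

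**What to change.** In SAP 10.7.1, replace the ratio with the difference in least square means (AMG 334 minus placebo) and its 95% confidence interval at each scheduled time. The difference exists at every hour with scores in both arms and corresponds to the null hypothesis already stated there. Bring the Appendix A1 code into line, and add an entry to SAP Section 11, because the protocol also specifies a ratio.

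The cost is one wording change, one changed estimate in the code and one line in Section 11. No new data and no design change are needed.

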10.7.2 Duration of Migraine-like Attacks (MLA) and Headaches

Descriptive statistics will be provided for the duration of MLA and headaches by treatment group.

10.7.3 Migraine Characteristics

Descriptive summaries of measured characteristics of MLA and headaches, such as localization and accompanying symptoms and pre-monitory symptoms, within 24 hours after infusion with PACAP-38 will be presented for each treatment group.

10.7.4 Plasma Concentration of PACAP-38 and CGRP

Summary statistics will be generated for plasma PACAP-38 and CGRP levels pre/post dosing with PACAP-38. Summaries will be produced by treatment group for the second dose of PACAP-38 (ie., the dose administered after administration of IP).

Statistical Analysis Plan: 20140207

Date: 17 May 2017 Page 26

10.8 Columbia Suicide Severity Rating Scale (C-SSRS)

Subject incidence of treatment-emergent suicidal ideation and behavior as assessed by C-SSRS will be reviewed and may be summarized.

10.9 Exposure to Investigational Product (IP)

Subject listings of manufacturing lot numbers and a separate listing of unique manufacturing lot numbers used in this study will be provided. Details for each AMG 334 administration will be listed for every subject.

10.10 Exposure to Non-Investigational Medicinal Product (NIMP)

Subject listings of PACAP-38 used in this study will be provided. Details for PACAP-38 administration will be listed for every subject.

10.11 Exposure to Concomitant Medication

All medication will be coded using the World Health Organization Drug (WHO DRUG) dictionary. All prior and concomitant medications will be reviewed.

11. Changes From Protocol-specified Analyses

Minor changes to the protocol-specified analyses have been made and clarified in this SAP.

The safety analysis set has been modified slightly to include all subjects who receive IP (AMG 334 or placebo), but excludes any reference to whether the subject receives PACAP-38 or not. This is to take into account any subjects that receive IP, but do not receive PACAP-38 (eg, subject withdrew from the study before PACAP-38 could be administered). In these cases, the subject's data will be reviewed, but will not be included in any data summaries.

ECG data will not be summarized as specified in the protocol, as the data was collected as part of the standard of care and not in a thorough manner.

12. Literature Citations / References

Headache Classification Subcommittee of the International Headache Society. The international classification of headache disorders, 2nd edition. *Cephalalgia*. 2004; 24(Suppl. 1):8-160.

13. Data Not Covered by This Plan

The following analyses will be analyzed outside of this SAP:

- The changes in plasma PACAP-38 and CGRP concentrations pre- and post-dosing with AMG 334
- Blood samples collected for biomarker development

Statistical Analysis Plan: 20140207 Date: 17 May 2017 Page 27

14. **Appendices**

Statistical Analysis Plan: 20140207

Date: 17 May 2017 Page 28

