If the PI, MM, and GSO or designee decides not to proceed with enrollment into a subsequent cohort, then a Safety Review Meeting or DLRM will be held after the last dosed cohort. The Safety Review Meeting or DLRM voting members will decide whether or not to proceed with enrollment in Part B Randomization (AMG 334 or Placebo) Phase and if the decision is made to proceed, the Safety Review Meeting or DLRM voting members will select the appropriate PACAP-38 dose from the Dose Selection Phase, Part A. The decision to proceed with Part B of the study will be based on the goal of ensuring subject safety and ideally triggering headache in all subjects within a given cohort and moderate to severe MLAs in the majority of subjects within the same cohort. However, the trigger of headaches in the majority of subjects within the same cohort and mild, moderate or severe MLAs in the majority of subjects within the same cohort may be considered acceptable to advance to Part B of the study.

Part B: Randomization (AMG 334 or Placebo) Phase: PACAP-38 responders from part A, as well as PACAP-38 naïve subjects (those who never received PACAP-38

Statistical Analysis Plan: 20140207

Dated: 17 May 2017 Page 9

before) can enter screening in part B. Subjects will be enrolled in Part B following the 21 day screening period. There will be a minimum duration of 2 weeks between the first and second PACAP-38 doses for all subjects enrolling in Part B of the study.

Eligible PACAP-38 responders from Part A will immediately be randomized to receive either AMG 334 or placebo, whereas eligible PACAP-38 naïve subjects will first enter a PACAP-38 challenge phase. Only PACAP-38 responders (those who experienced a MLA within 24 hours after the challenge) will be randomized to receive either AMG 334 or placebo.

A minimum of 16 and a maximum of 36 PACAP-38 responders will be randomized to receive AMG 334 or Placebo.

PACAP-38 Responders from Part A

On Day 1, PACAP-38 responders from Part A will receive 140 mg IV AMG 334 over 30 minutes or placebo, in a one to one allocation ratio. On Day 8, the subjects will be administered the dose of PACAP-38 determined from the PACAP-38 Dose Selection Phase (Part A).

PACAP-38 Naïve Subjects

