7.1 Safety Analysis Set

The safety analysis set will consist of all subjects who receive IP (AMG 334 or placebo). Subjects will be analyzed according to the IP received (AMG 334 or Placebo).

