10.1 General Principles

Unless otherwise stated, data from PACAP-38 responders who go on to be randomized and receive IP will be summarized. Data from PACAP-38 non-responders, and data from

Statistical Analysis Plan: 20140207

Date: 17 May 2017 Page 22

PACAP-38 responders that do not receive IP, will not be included in the summaries, but will be reviewed.

Unless otherwise specified, data will be summarized using the safety analysis set, by actual treatment group (AMG 334 or Placebo).

Descriptive statistics will be provided for selected demographics, safety and PK data. Descriptive statistics on continuous measurements will include means, medians, standard deviations (and standard errors for post-baseline data), quartiles, and ranges, while categorical data will be summarized using frequency counts and percentages. Where statistical models are applied to the data, estimates of the differences/ratios, confidence intervals and corresponding p-values will be presented, as applicable. However, these are for descriptive and illustrative purposes only and to aid interpretation of the data; no formal statistical hypothesis testing will be performed.

When data are summarized by time, the values recorded against the scheduled time points, including any time windows specified in the protocol will be used.

When assessing minimum/maximum increases or decreases over the study, all assessments, including unscheduled assessments will be used.

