10.6.2 Safety Endpoints

10.6.2.1 Adverse Events (AEs)

The Medical Dictionary for Regulatory Activities (MedDRA) version 19.1 or later will be used to code all AE to a system organ class and a preferred term. The subject incidence of AEs will be summarized for all treatment-emergent, serious treatment-emergent, those leading to withdrawal of IP, fatal, and events of interest (EOI), where treatment refers to IP. The identification of EOI is a continuous process. Events may be identified and documented as the safety profile of the drug is characterized. The severity of each AE will be graded using common terminology for AE (CTCAE) version 4.0 criteria.

Statistical Analysis Plan: 20140207

Date: 17 May 2017 Page 24

Subject incidence of all treatment-emergent, serious treatment-emergent, those leading to withdrawal of IP, and fatal AE will be tabulated by system organ class and preferred term, where treatment refers to IP. Where appropriate, the tables will also be presented by worst grade. The above AE tables will not be created if two or fewer subjects experience the AE. The above AE tables will be summarized separately for events occurring between Day 1 and Day 7 following administration of IP and events occurring from Day 8 onwards following administration of IP and the second dose of PACAP-38.

For PACAP-38 related treatment-emergent AEs, all treatment-emergent AEs where the question "Is there a reasonable possibility that the event may have been caused by PACAP-38?" is ticked "yes" will be summarized by treatment group.

Details of each AE will be listed.

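### SAP Section 11 keeps subjects who receive AMG 334 or placebo but miss the later PACAP-38 challenge out of every summary, so the AMG 334 safety tables depend on reaching that challenge

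*SAP*

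**What the plan says.** SAP 7.1 sets no challenge condition: "The safety analysis set will consist of all subjects who receive IP (AMG 334 or placebo"). SAP 10.1 makes that set the default: "Unless otherwise specified, data will be summarized using the safety analysis set, by actual treatment group (AMG 334 or Placebo").

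SAP Section 11 describes this as a change from the protocol and gives the reason: "This is to take into account any subjects that receive IP, but do not receive PACAP-38". Its example is a subject who withdraws before the infusion. The next sentence reads "In these cases, the subject's data will be reviewed, but will not be included in any data summaries".

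The supplied protocol (Amendment 3) required both IP and PACAP-38 for the safety set (10.1.2.1) and kept subjects with IP only in listings (10.5.1).

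SAP 10.6.2.1 plans AE tables "summarized separately for events occurring between Day 1 and Day 7 following administration of IP" and, apart from these, for "events occurring from Day 8 onwards following administration of IP and the second dose of PACAP-38". SAP 10.6.2.2 plans heart rate and blood pressure summaries, 10.6.2.5 a summary of liver abnormalities, and 10.6.4 antibody incidence by treatment group. SAP 2.2 makes the safety, tolerability, pharmacokinetics and immunogenicity of one IV dose of AMG 334 a secondary objective.

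On which PACAP-38 dose is meant, SAP 3.1 states: "Only PACAP-38 responders (those who experienced a MLA within 24 hours after the challenge) will be randomized to receive" AMG 334 or placebo. SAP 10.7.4 names the dose clearly for its own summaries: "the second dose of PACAP-38 (ie., the dose administered after administration of IP").

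**The concern.** The secondary safety objective concerns AMG 334 and does not need the challenge. Reaching the challenge, about a week after IP, is a post-dose event. It can be missed through withdrawal, and withdrawal can follow from an adverse event. Limiting safety tables to subjects who reached it can therefore select on the outcome being measured.

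The effect is clearest in the Day 1 to 7 AE table, which is the one that shows AMG 334 before the post-IP PACAP-38 dose is given. A subject who stops in that week because of an AE leaves both the numerator and the denominator. The supplied protocol asks subjects who stop treatment to continue safety visits (7.2.4) and those who terminate early to return for end-of-study assessments (7.2.5), so data that are meant to be collected would go unsummarised.

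**Working it through.** The plan gives no figure on this point, so the check compares the rules and then illustrates with counts.

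**1. Who is excluded.** Under SAP 3.1 every randomised subject has already had one PACAP-38 dose. Read literally, a rule about subjects who get no PACAP-38 would exclude nobody. Section 11's own example shows that the dose after IP is meant.

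**2. Which population is summarised.**

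| Source | IP and post-IP challenge | IP only |
|---|---|---|
| Protocol 10.1.2.1 with 10.5.1 | in the set, summarised | not in the set, listed |
| SAP 7.1 with Section 11 | in the set, summarised | in the set, not summarised |

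The set differs between the two rows. The summarised population does not.

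**3. Effect on an incidence.** In one arm let *n* be the IP recipients, *u* those not challenged, *x* those with the AE, and *a* those with the AE who were not challenged. On all IP recipients the incidence is *x/n*. Under Section 11 it is (*x* − *a*)/(*n* − *u*).

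Take one unchallenged subject with an AE that no one else in the arm had (*u* = *a* = *x* = 1):

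- Full trial of 18 per arm, not replaced: 1/18 = 5.6% becomes 0/17 = 0%.
- Full trial, replaced, so that 18 are challenged: 1/19 = 5.3% becomes 0/18 = 0%.
- Stopped at the interim: SAP 8.2 runs the interim once 8 per group have 24 hours of data after the Day 8 infusion, so 8 per arm are challenged and the ninth is the unchallenged subject. Then 1/9 = 11.1% becomes 0/8 = 0%.

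Both replacement cases are shown because the supplied protocol is not uniform: 3.4 provides for replacing subjects lost before PACAP-38, at the discretion of the medical monitor and investigator, while 5.1 limits replacement during the study to reasons other than adverse events.

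The effect can go the other way. With *n* = 18, *x* = 5, *u* = 1, *a* = 0, 5/18 = 27.8% becomes 5/17 = 29.4%.

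**4. How often it could arise.** The documents give no rate of IP recipients who miss the challenge. Assuming an independent chance *p* per subject, the chance of at least one among 18 in the AMG 334 arm is 1 − (1 − *p*)^18: 30% at *p* = 2%, 60% at 5%, 85% at 10%. These are assumed rates, not forecasts. Protocol 2.2.2.1 reports that all 60 dosed subjects in the first-in-human single-dose study completed it.

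**5. Table threshold.** SAP 10.6.2.1 creates no table when two or fewer subjects have the AE. Taking the threshold to apply to each table, one or two serious, fatal or withdrawal AEs are listed only, with or without the Section 11 rule. Dropping one subject with such an AE removes a table only when the count falls from 3 to 2. The counts in step 3 then apply to rows of tables that are produced.

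**The case against.** The rule is disclosed, pre-specified and carried over from the protocol, and the opening words of the SAP 10.1 default allow exceptions, so Section 11 can formally override it. No record is lost: SAP 10.6.2.1 lists every AE, and SAP 10.2 counts IP recipients and discontinuations with reasons and reviews the timing of early withdrawals. Little scheduled data is at risk. In the supplied protocol's Table 2, vital signs between IP and Day 8 are taken only at 0.5 and 1 hour, and no chemistry is drawn before the Day 8 pre-dose sample. There may be no such subject at all.

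All of this stands, and it limits the size. It does not repair incidence tables that a reader will take to describe AMG 334 recipients.

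Some stronger readings are tempting but not supported:

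- **1/8 reported as 0/7.** A reader might infer this for a trial stopped at the interim. The SAP 8.2 trigger needs 8 challenged subjects per group, so the matching case is 1/9 to 0/8.
- **PK parameters lost.** Taken literally, Section 11 would also reach the one-hour AMG 334 concentration. But SAP 10.6.3 specifically assigns the PK analysis set, which SAP 7.2 defines without a challenge condition. A clarifying sentence is enough.
- **AEs miscounted around Day 8.** Protocol 7.2 of Amendment 3 allows the challenge up to 4 days late, so a Day 12 challenge would leave Days 8 to 11 before it. The SAP follows Amendment 4, which was not supplied. The SAP wording could also be read as requiring the second dose, in which case those events fall in neither table. The point is conditional.
- **Bias in favour of AMG 334.** The direction is not established; step 3 shows both.

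**Conclusion.** The concern holds on SAP text alone. Sections 7.1 and 11 widen the safety set with a particular group in mind, and Section 11 then removes that group from every summary. The AE tables, the heart rate and blood pressure summaries, any laboratory or liver summaries and the antibody incidence are therefore conditioned on reaching the post-IP challenge.

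For one affected subject with an otherwise unseen AE, an incidence of about 5% in a full trial, or 11% in one stopped at the interim, is tabulated as 0%. This assumes that at least one IP recipient misses the challenge; if none does, the effect is nil. The number and the direction are unknown. The events would be absent from the incidence tables, not from the record.

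The remarks on protocol 10.5.1, replacement, follow-up visits and the visit window rest on Amendment 3 and need checking against Amendment 4.

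**What to change.** - Limit the Section 11 exclusion to the challenge-dependent analyses: MLA, headache, severity, duration, migraine characteristics and post-challenge PACAP-38 and CGRP levels. Define a challenge set for them: subjects given IP and the post-IP (second) PACAP-38 dose.
- On all IP recipients with data, summarise pre-challenge AEs, one overall post-IP AE table, heart rate and blood pressure, any laboratory or liver summaries, and antibody incidence.
- Footnote the number not challenged, with reason, by arm.
- Reword Section 11 so that it names the post-IP (second) dose of PACAP-38, and state that it does not override the PK set assigned in SAP 10.6.3.
- If Amendment 4 keeps the 4-day challenge window, split AEs at each subject's actual challenge date rather than at Day 8. If it keeps the listing-only sentence of protocol 10.5.1, align that too.

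The cost is SAP wording and light table programming on data already planned for collection. The downside is different denominators for safety and challenge analyses, which the footnote explains.
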